#### 5.2 Subject Exclusion Criteria

An individual who meets any of the following criteria will be excluded from participation in this study:

- 1. Subject is pregnant, or lactating, or of childbearing potential (to be considered of non-childbearing potential, a female must be post-menopausal for at least 1 year, surgically sterile, or using an effective method of contraception or abstinence from at least 4 weeks prior to the first vaccination and until at least 4 weeks after the last vaccination.
- 2. Participation in the 4 weeks preceding the first trial vaccination, or planned participation during the present trial period, in another clinical trial investigating a vaccine, drug, medical device, or medical procedure.
- 3. Previous history of receiving the rabies vaccine.
- 4. Previous history of receiving rabies immune globulin.
- 5. Any major psychiatric disorder, such as severe depression, severe anxiety disorder, psychosis, schizophrenia, other major psychiatric disorders, or seizures. History of mild depression or anxiety disorder that are well controlled are not exclusion criteria.

MALRAB Version 11.0 09 May 2018

6. Use of any immunosuppressive drug at the time of the study or 30 days previously. Topical steroids will not be considered an immunosuppressive drug and their use will not be considered an exclusion criteria.

- 7. Any immunosuppressive disorder, such as HIV infection, common variable immunodeficiency, active cancers or chemotherapy.
- 8. History of renal insufficiency or requiring dialysis.
- Have any condition that would, in the opinion of the site investigator, place the subject at an unacceptable risk of injury or render the subject unable to meet the requirements of the protocol.
- 10. Previous adverse reaction to any of the antimalarial drugs used in this study.

Temporary Exclusion Criteria: Moderate or severe acute illness/infection (according to investigator judgment) or febrile illness (temperature ≥ 38.0°C [≥ 100.4°F]) on day 0.. A prospective subject should not be included in the study until the condition has resolved or the febrile event has subsided. If the delay for the febrile illness exceeds the window between screening and vaccination, or if deemed necessary by the investigator, a prospective subject may be re-screened once the fever has resolved.

Recent or scheduled receipt of any vaccine 4 weeks prior to day 0.

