## 8.2 Laboratory Assays

## 8.2.1 Rapid Fluorescent Foci Inhibition Test (RFFIT)

RFFIT is a serum neutralization (inhibition) test, which means it measures the ability of rabies specific antibodies to neutralize rabies virus and prevent the virus from infecting cells. These antibodies are called rabies virus neutralizing antibodies (RVNA).

The World Health Organization (WHO) guideline of 0.5 International Units per milliliter (IU/mL) is used as an adequate response to rabies vaccination, as well as the ACIP level of "complete neutralization at a serum dilution of 1:5 in the RFFIT test" as evidence of adequate response in a person.

RFFIT analysis will be performed on samples taken from Day 0, prior to vaccination 3, prior to vaccination 4, 14 and 28 days post 4th vaccination.

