## Per Protocol Analysis Set

The Per-Protocol (PP) analysis set will include all subjects who had no protocol deviations at the time that the data was collected. Two PP analysis sets will be produced for the primary objective that will contain separate data from blood drawn on day 0 and 14 days post 4th vaccination. Descriptive analysis of the secondary endpoint will require three additional per protocol analysis sets for blood drawn prior to 3rd and prior to 4th vaccination and on day 28 post 4th vaccination.

Subjects will be excluded from the PPAS for the following reasons:

- 1. Subject did not meet all protocol-specified inclusion/exclusion criteria or experienced a definitive contraindication
- 2. Administration of vaccine was not done per protocol
- 3. Subject did not receive vaccine in the proper time window as defined in the study procedures
- 4. Subject did not provide a post-dose serology sample in the proper time window as defined in the study procedures\*
- 5. For the malarone and doxycycline groups, subject missed the three or more of the daily dose of antimalarial in any one week.
- 6. For the chloroquine group, subject missed their weekly dose by three or more days

For the computation of GMTs, a titer reported as < LLOQ will be converted to a value of 0.5 LLOQ.

For calculating fold-rise and titer ratio (GMTR), < LLOQ will be converted to 0.5 LLOQ for a numerator and < LLOQ will be converted to LLOQ for a denominator

Any titer reported as > ULOQ (upper limit of quantization) will be converted to ULOQ.

Missing data will not be imputed.

\*Subjects whose serology sample is outside the defined window for the secondary endpoint will still be included in the primary endpoint analysis.

·

Potential outliers will be identified using histograms and modified box plots or normal probability plots, when appropriate. Choice of subsequent tests for outliers (e.g. Grubbs, Tietjen-Moore and ESD) will depend on the number and nature of suspected outliers and may require data transformation. Bootstrapped estimates of standard errors may also be reported. Sensitivity analysis of effect of outliers on descriptive statistics will be conducted, and if necessary descriptive statistics that include and exclude outliers will be reported

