A descriptive summary of adverse events and serious adverse events that were reported throughout the trial will be produced.

Descriptive and inferential analyses (if any) will be carried out using SAS Version 9.4 (or more recent versions), which is licensed and supplied by SAS Institute, Cary, NC, USA.

Per-Protocol Analysis Set

The Per-Protocol analysis set (PPAS) will include all subjects who had no protocol deviations at the time that the data was collected. Two PP analysis sets will be produced for the primary objective that will contain separate data from blood drawn on day 0 and 14 days post 4th vaccination. Descriptive analysis of the secondary endpoint will require three additional per protocol analysis sets for blood drawn prior to 3rd and prior to 4th vaccination and on day 28 post 4th vaccination.

Subjects will be excluded from the PPAS for the following reasons:

- 1. Subject did not meet all protocol-specified inclusion/exclusion criteria or experienced a definitive contraindication
- 2. Administration of vaccine was not done per protocol
- 3. Subject did not receive vaccine in the proper time window as defined in the study procedures
- 4. Subject did not provide a post-dose serology sample in the proper time window as defined in the study procedures*
- 5. For the malarone and doxycycline groups, subject missed the three or more of the daily dose of antimalarial in any one week.

6. For the chloroquine group, subject missed their weekly dose by three or more days

*Subjects whose serology sample is outside the defined window for the secondary endpoint will still be included in the primary endpoint analysis.

Subjects will be analyzed by the vaccine group to which they were randomized, subject to the exclusion criteria above

Handling of Missing Data and Outliers

For the computation of GMTs, a titer reported as < LLOQ will be converted to a value of 0.5 LLOQ.

For calculating fold-rise and titer ratio (GMTR), < LLOQ will be converted to 0.5 LLOQ for a numerator and < LLOQ will be converted to LLOQ for a denominator

Any titer reported as > ULOQ (upper limit of quantization) will be converted to ULOQ.

Missing data will not be imputed.

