Potential outliers will be identified using histograms and modified box plots or normal probability plots, when appropriate. Choice of subsequent tests for outliers (e.g. Grubbs, Tietjen-Moore and ESD) will depend on the number and nature of suspected outliers and may require data transformation. Bootstrapped estimates of standard errors may also be reported. Sensitivity analysis of effect of outliers on descriptive statistics will be conducted, and if necessary descriptive statistics that include and exclude outliers will be reported

Statistical Methods for Baseline Comparisons

Mean (SD) and median (IQR) age at baseline will be computed and descriptively compared across the six groups. Results will be presented in tabular format. Baseline mean (SD) and median (IQR) of all other quantitative demographic variables of interest at baseline will be calculated for each group and the results will be presented in a table.

The number and percentage of males and females per group at baseline will be calculated and results will be presented in tabular format. The number and percentage per group at baseline of all other qualitative demographic variables of interest will be calculated for each group and the results will be presented in tabular format.

Statistical Methods for Subject Disposition

For each group (three prophylaxis and one control), the number and percentage of subjects who received a total of 0, 1, 2, 3 and 4 rabies vaccinations will be reported in tabular format.

For each group, a line listing of subjects who discontinued the study that includes classification of the most serious reason for termination will be produced.

Statistical Methods for Primary Immunogenicity Objectives

Primary Objective: Compare GMT at 14 days post completion of four dose PEP with PCECV in each of the malaria prophylaxis groups with control to determine if a fifth dose of PEP at that point would be of any added value.

Immunogenicity against rabies will be assessed descriptively using the following parameters:

Timepoints: At 14 days post-completion of four doses of rabies vaccine

 Geometric mean titer (GMT) against rabies virus for the prophylaxis and control groups at 14 days after completion of four doses of vaccine.

A table that presents the total number of per-protocol subjects and GMT against rabies at 14 days post completion of four doses of vaccine by group will be produced.

Statistical Methods for Secondary Immunogenicity Objectives

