Secondary Objective: To evaluate GMT over protective titer prior to third dose, fourth dose and 28 days post fourth dose of PCECV.

Immunogenicity will be assessed descriptively using the following parameters:

Timepoints: prior to third and fourth dose of rabies vaccine and 28 days after fourth dose of vaccine

A table that presents, by group, the total number of per protocol subjects and the GMT against rabies prior to the third and fourth dose of vaccine and 28 days after fourth dose of vaccine will be produced.

Statistical Methods for Adverse Events and Serious Adverse Events

For each treatment group, a line listing by subject that describes adverse events and post-baseline day of occurrence of the AE will be produced.

The number and percent of subjects in each group who reported any AE between Days 0 and 372 will be summarized in tabular format.

A table showing the number and percentage of subjects in each group who reported adverse events by general type (category) of event will be produced.

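### Does the below-LLOQ rule for fold-rise and GMTR (half the LLOQ on top, the full LLOQ underneath) distort the comparison of the groups?

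*SAP*

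**What the plan says.** Protocol 12.3 (Per Protocol Analysis Set) and the SAP (Handling of Missing Data and Outliers) carry the same two rules for titres below the LLOQ.

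- **GMTs:** "For the computation of GMTs, a titer reported as < LLOQ will be converted to a value of 0.5 LLOQ".
- **Ratios:** "For calculating fold-rise and titer ratio (GMTR), < LLOQ will be converted to 0.5 LLOQ for a numerator", with the full LLOQ used in a denominator. The SAP states the pair as "< LLOQ will be converted to 0.5 LLOQ for a numerator and < LLOQ will be converted to LLOQ for a denominator".

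Neither document says what is divided by what in GMTR. It could be antimalarial over control, or a later visit over an earlier one. The abbreviation list has GMT but not GMTR, and no LLOQ value is given.

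The outputs are narrower than the rule. Protocol 3.2.1 and 3.2.2 define the endpoints as GMTs. The SAP's primary table holds "the total number of per-protocol subjects and GMT against rabies at 14 days post completion", by group. Its secondary table holds N and "the GMT against rabies prior to the third and fourth dose of vaccine", plus the GMT 28 days after dose 4. No table of fold-rise or GMTR is specified. A Day 0 data set is planned, however: "Two PP analysis sets will be produced for the primary objective that will contain separate data from blood drawn on day 0" and, separately, from 14 days after dose 4.

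**The concern.** One sample would carry two values: half the LLOQ in the GMT table and the full LLOQ in the denominator of a ratio. Two things follow.

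1. A subject undetectable at both visits is given a fold-rise of 0.5, an apparent halving where no change was seen.
2. If GMTR is antimalarial over control, two identical groups would not give a ratio of 1 whenever some controls are below LLOQ. The ratio would fall below the quotient of the tabulated GMTs, towards impairment by the antimalarial, which is the effect under study.

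The samples most exposed are those before dose 3, seven days after the first vaccination. Protocol 8.2.1 includes them: "RFFIT analysis will be performed on samples taken from Day 0, prior to vaccination 3". A rule written for ratios, a Day 0 set and a provision for exploratory analyses together suggest that ratios might be reported.

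**Working it through.** The documents give no figure to reproduce here. The check is algebra on the two rules. The LLOQ cancels, so its value is not needed.

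**Inputs.** Substitution is 0.5 LLOQ for GMTs, and 0.5 LLOQ over LLOQ for ratios (protocol 12.3 and SAP). Group size is 25 (protocol section 5), used for illustration because per-protocol sets may be smaller. The share of titres below LLOQ is not given, so a range is shown.

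**One subject, Day 0 below LLOQ.**

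- Later titre also below LLOQ: 0.5 LLOQ / LLOQ = 0.5. With half the LLOQ on both sides it would be 1.
- Later titre 10 × LLOQ: 10 under the plan's rule, 20 with half the LLOQ on both sides.

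Both values are halved. The second subject stands at 10/0.5 = 20 times the first under the plan's rule, and at 20/1 = 20 times under the symmetric rule. The 0.5 is the same scaling applied to everyone with an undetectable baseline.

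**Between-group reading, control as denominator (an assumption).** If k of 25 controls are below LLOQ, using LLOQ in place of 0.5 LLOQ multiplies the control geometric mean by 2^(k/25). Hence

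GMTR = (GMT antimalarial / GMT control) × 2^(−k/25).

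| k of 25 controls below LLOQ | Multiplier |
|---|---|
| 0 | 1.00 |
| 1 | 0.97 |
| 2 | 0.95 |
| 5 | 0.87 |
| 10 | 0.76 |
| 20 | 0.57 |
| 25 | 0.50 |

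The multiplier depends only on the share below LLOQ, not on the spread of titres. With the ratio turned over (control / antimalarial), the same rule lowers control relative to antimalarial and so shifts the result away from impairment.

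**Within-subject reading (later visit / Day 0).** Let a and b be the numbers of Day 0 titres below LLOQ in the antimalarial and control groups. Relative to half the LLOQ on both sides, the ratio of the two groups' mean fold-rises is multiplied by 2^(−(a−b)/25):

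- a = 25, b = 25: 1.00
- a = 24, b = 25: 2^(1/25) = 1.03
- a = 25, b = 23: 2^(−2/25) = 0.95

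Protocol 5.2 excludes anyone with "Previous history of receiving the rabies vaccine", so Day 0 should be below LLOQ in nearly everyone (an inference). If it is so in everyone, each group's mean fold-rise is its later GMT divided by LLOQ, and the ratio of fold-rises equals the quotient of the tabulated GMTs exactly.

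**An obvious repair, tested.** Suppose the LLOQ denominator were kept but the ratio set to 1 when both titres are below LLOQ. That raises only the non-responders. With all Day 0 titres below LLOQ, and 5 of 25 antimalarial against 0 of 25 control subjects still undetectable later, the ratio of fold-rises becomes the GMT quotient × 2^(5/25) = 1.15. This would mask impairment where the existing rule gives 1.00.

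**The case for a change.** The best case for acting is that the rule is either used or idle. If it is used, a between-group ratio is a natural way to express the primary comparison, and it would contradict the GMT table for the same samples. If it is idle, it should go. A wish to be conservative explains the LLOQ denominator for fold-rise when the later titre is detectable. It does not explain a value below 1 for no observed change, nor a between-group ratio pushed towards the effect under study. The remedy would be a sentence or two.

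The algebra stands, and so does the point that GMTR is undefined. An LLOQ denominator does not suit a between-group ratio. But the rule puts GMTR beside fold-rise and substitutes values titre by titre, and a Day 0 set is planned, so the within-subject reading is at least as natural. The direction of bias holds only with control underneath. The large factors need 20 or more of 25 controls undetectable, and the documents give no rate to support that.

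Nor is symmetric substitution a clear gain for fold-rise. It doubles every fold-rise from an undetectable baseline, and the result is no longer a lower bound.

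**Conclusion.** No change to the plan follows. The primary and secondary results are GMTs by group under one symmetric substitution, and the ratio rule alters none of them.

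For fold-rise from Day 0, the rule is a fair trade-off: a conservative convention that leaves group comparisons unchanged if Day 0 is below LLOQ in everyone, and moves them by 3% to 5% if one or two subjects in one group are the exception.

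For a between-group ratio, the undefined GMTR is a gap that an analyst fills sensibly by dividing the GMTs already in the table. A ratio built under the other rule would visibly fail to match that table. Its error would be 2^-p: none if no denominator titre is below LLOQ, 3% for one of 25, and at most a factor of 2. Fourteen days after dose 4 it is small if few titres are below LLOQ.

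This rests on two assumptions the documents do not confirm: that Day 0 titres are nearly all below LLOQ, and that no ratio becomes a main result. If a between-group GMTR were reported as a main result before dose 3, with many controls undetectable, the concern would have substance.

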#### **3 OBJECTIVES AND ENDPOINTS**

## 3.1 Study Objectives

#### 3.1.1 Primary Study Objective

To compare Geometric Mean Titer (GMT) at 14 days post completion of four dose post exposure prophylaxis (PEP) with PCECV in each of the malaria prophylaxis groups with control to determine if a fifth dose of PEP at that point would be of any added value.

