# 3.2 Study Endpoints

# 3.2.1 Primary Endpoint (Immunogenicity)

GMT by RFFIT at 14 days post completion of four doses PEP in prophylaxis groups vs. control group.

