#### 5.4.1 Randomization Procedures

The randomization schedule will be generated by the statistician using SAS 9.3 PROC PLAN. Variable block sizes will be kept confidential from the clinical staff to reduce the predictability of the treatment assignments. Subjects who withdraw prior to first vaccination will be replaced by the next enrolled subject who will be assigned to the same group as the withdrawn subject.

The first 39 subjects would be randomized to malarone, doxycycline and control group (1:1:1). Subjects 40-100 would be randomized to chloroquine, malarone, doxycycline and control groups (2:1:1:1). This would ensure that upon completion of enrollment

·

subjects would be randomly allocated 1:1:1:1 across all four groups - three treatment groups and one control group.

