STUDY TITLE: Effect of Antimalarial Drugs on the Immune Response to Rabies Vaccine for Post-exposure Prophylaxis. A Randomized, Open Label, Trial in Healthy US Adults Age 18-60 Years

NCT#: 02564471

DOCUMENT DATE: 10 January 2017

Effect of Antimalarial Drugs on the Immune Response to Rabies Vaccine for Post-exposure Prophylaxis

A Randomized, Open Label Trial in Healthy US Adults Ages 18-60 Years

Statistical Analysis Plan (SAP) Version 1.0, Dated 10 Jan 2017

Funder: MILVAX

[name]

Walter Reed Army Institute of Research

[name] [name] 20910

Principle Investigator: [name]

Upstate Medical University [name] Syracuse, NY 13210

Licensed Products: RabAvert® Rabies Vaccine

Chloroquine Malarone Doxycycline

Research Monitor: [name]

Upstate Medical University [name] Syracuse, NY 13210

Study Site/PI Location: Center for Global Health and Translational Science

Upstate Medical University [name] Syracuse, NY 13210

Study Statistician and [name]

SAP Author: Associate Professor, Department of Health and Preventive Medicine

SUNY Upstate Medical University

[name] Syracuse, NY 13210

Statistical Methods

The analysis will be performed under the responsibility of Upstate Medical University in conjunction with the study partners.

This will be a descriptive study to assess immunogenicity of a licensed rabies vaccine using test dosage schedules in the presence of malaria chemoprophylaxis. No formal statistical hypothesis tests will be conducted. Descriptive analyses will be based on the per-protocol analysis sets using the RFFIT data from blood samples taken samples taken from Day 0, prior to vaccination 3, prior to vaccination 4, 14 and 28 days post 4th vaccination. Separate descriptive analyses will be conducted for each per-protocol data set and group.

Exploratory statistical analyses of final data may be conducted, if indicated by the descriptive results. Parametric, non-parametric and resampling (bootstrapping) methods for statistical inference may be used in exploratory analyses, based on data compliance with assumptions of methods. P -values \leq 0.05 will be considered significant and p-values \leq 0.10 will be considered a trend. Confidence intervals will be constructed at α =0.05 and α =0.10. When necessary, p-value corrections for multiple comparisons will be applied.

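### The SAP's only specified primary output is per-protocol N and GMT by group; no ratio or interval is tied to the contrast of each antimalarial group with control

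*SAP*

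**What the plan says.** Protocol 3.1.1 makes the primary aim a comparison of GMT in each antimalarial group with control 14 days after dose 4, "to determine if a fifth dose of PEP at that point would be of any added value". The endpoint in Protocol 3.2.1 is worded as a contrast too: "GMT by RFFIT at 14 days post completion of four doses PEP in prophylaxis groups vs. control group". The SAP, under Statistical Methods for Primary Immunogenicity Objectives, restates the objective, lists a single parameter (the GMT in each group) and a single output: "A table that presents the total number of per-protocol subjects and GMT against rabies at 14 days post completion of four doses", by group. Protocol 12.3 adds only that each data set and group gets its own descriptive analysis.

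Ratios and precision are mentioned in three other places:

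- SAP, Statistical Methods, and Protocol 12.1: intervals are foreseen at alpha 0.05 and 0.10, but in a paragraph that opens "Exploratory statistical analyses of final data may be conducted, if indicated by the descriptive results". No parameter or contrast is named. The same paragraph attaches a significance label at 0.05 and a trend label at 0.10, although the text just before it rules out formal hypothesis tests.
- SAP, Handling of Missing Data and Outliers, in the outlier text: "Bootstrapped estimates of standard errors may also be reported".
- The same SAP section, in the rule for titres below the LLOQ: "For calculating fold-rise and titer ratio (GMTR), < LLOQ will be converted to 0.5 LLOQ for a numerator". The rest of that rule, also in Protocol 12.3, reads: "< LLOQ will be converted to LLOQ for a denominator". Neither the groups nor the time point of the ratio is given.

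On allocation, Protocol 5.4.1 says: "The first 39 subjects would be randomized to malarone, doxycycline and control group (1:1:1". Subjects 40 to 100 are then allocated 2:1:1:1, with chloroquine taking the double share. The SAP (10 January 2017) does not mention this staging; the protocol that describes it is Version 11.0 (9 May 2018).

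**The concern.** The objective is a contrast, but the required output is four separate numbers. A reader can divide two GMTs, yet cannot tell from the table how large a reduction against control remains compatible with the data. That is what a reader needs when the stated purpose is to judge the value of a fifth dose. Protocol 12.2 says the study is not powered for equivalence or non-inferiority, so similar GMTs printed without intervals could be read as more reassuring than they are. Leaving the ratio and the confidence level to be settled after the descriptive results are seen also leaves room for selective reporting in an open-label trial.

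The chloroquine contrast raises a second question. Controls among the first 39 subjects had no chance of being assigned chloroquine. The SAP does not say whether they enter that comparison.

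**Working it through.** **The plan's own figures.** Protocol 12.2 gives 100 subjects, 1:1:1:1, chosen empirically. There is no SD, effect size, power or dropout rate, so there is no power calculation to reproduce. The allocation arithmetic can be checked against Protocol 5.4.1:

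- Stage 1: 39 / 3 = 13 each to Malarone, doxycycline and control.
- Stage 2: 61 subjects at 2:1:1:1 give 61 × 2/5 = 24.4 to chloroquine and 61 / 5 = 12.2 to each other group.
- Expected totals: 24.4 chloroquine; 13 + 12.2 = 25.2 in each other group. This agrees with the planned 25.
- So about 13 of about 25 controls precede chloroquine allocation, and about 12 are concurrent with it.

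**Precision of one GMT ratio.** The SD of log10 titre is an assumption, taken over 0.3 to 0.6. For a two-sample t interval on log10 titres:

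factor = 10^( t(0.975, n1 + n2 − 2) × SD × √(1/n1 + 1/n2) )

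The 95% interval is the estimated ratio divided and multiplied by this factor. If the two observed GMTs are equal, the largest reduction not excluded is 1 − 1/factor. For example, at 25 versus 25 and SD 0.3: 2.011 × 0.3 × √(2/25) = 0.171, and 10^0.171 = 1.48. The interval is 0.68 to 1.48, so a 32% reduction is not excluded.

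| Comparison | t | SD 0.3 | SD 0.4 | SD 0.5 | SD 0.6 |
|---|---|---|---|---|---|
| 25 vs 25 | 2.011 | 1.48 (32%) | 1.69 (41%) | 1.92 (48%) | 2.19 (54%) |
| 20 vs 20 (assumed per-protocol loss) | 2.024 | 1.56 (36%) | 1.80 (45%) | 2.09 (52%) | 2.42 (59%) |
| Chloroquine vs concurrent controls, 24 vs 12 | 2.032 | 1.64 (39%) | 1.94 (48%) | 2.29 (56%) | 2.70 (63%) |

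The 90% factors at 25 versus 25 are 1.39, 1.55, 1.73 and 1.93.

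**The LLOQ rule in a between-group ratio.** The GMT table uses 0.5 LLOQ for every value below the LLOQ. If the ratio rule were applied with control as denominator, a control value below the LLOQ would count as LLOQ, twice its value in the table. With a fraction p of control titres below the LLOQ, the control GMT rises by 2^p, so the ratio is multiplied by 2^(−p) relative to the ratio of the tabulated GMTs. At p = 10% this is 2^(−0.1) = 0.93, about 7% lower, against the antimalarial group. At the primary time point p is probably small, so the effect is probably small too.

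**The case against.** The strongest reply is that the study is declared exploratory and descriptive, disclaims power for equivalence and non-inferiority, and already foresees intervals, a titre ratio and standard errors. On this view nothing is missing except cross-references. Part of this stands. A reader might infer that the plan has no interval or ratio at all; that is not so. But the interval sentence sits in a conditional paragraph and names no contrast, the ratio appears only in a substitution rule, and the standard errors are optional. None of them tells the analyst what to report for the primary comparison. Nor does the descriptive status explain the gap: a ratio with an interval is an estimate, not a test.

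A second reply is that non-concurrent controls are a separate matter and that no drift mechanism is offered: the subjects are healthy adults at one site, and the protocol lists one vaccine lot. That is fair as to bias. A reader might infer that the chloroquine result is biased, or that the SAP knowingly ignored the staging. The documents support neither. The SAP predates the protocol version under review, and when staging was introduced is not shown. A reader might also take chloroquine to be the drug the trial is about. Protocol 2.2 gives it as the drug with earlier evidence, with Malarone and doxycycline as those most often prescribed to deploying soldiers.

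Third, every interval above rests on an assumed SD. That is correct; the figures illustrate scale and do not measure this trial's precision.

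**Conclusion.** The point holds as a gap in specification that should be fixed. Followed as written, the primary analysis yields per-protocol N and GMT by group and leaves the precision of each contrast with control unreported. Under an assumed log10 SD of 0.3 to 0.6 and 25 per group, equal GMTs would leave a 32% to 54% reduction not excluded; against concurrent controls only, the range for chloroquine is 39% to 63%. The specification gap is certain from the text; its size depends on the assumed SD and, for the smaller case, on an assumed 20 per group.

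The pooled chloroquine contrast is only partly concurrent, which justifies a sensitivity estimate and no more. A reader might go on to infer that 100 subjects is too few, or that multiplicity-adjusted tests are required. Neither follows: the plan sets no margin or power target and claims no formal test.

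**What to change.** 1. In the SAP's primary section, add a 95% interval to each group GMT. For each antimalarial group versus control at 14 days after dose 4, add the GMT ratio with an unadjusted 95% interval from log10 titres, labelled descriptive. State in SAP Statistical Methods and Protocol 12.1 (and in the Synopsis, which repeats the paragraph) that the significance and trend labels do not apply to these three ratios, and that 90% intervals, if shown, are supplementary.
2. Add a descriptive sensitivity ratio for chloroquine versus control, limited to subjects enrolled after chloroquine allocation opened. Say how replacement subjects are handled: under Protocol 5.4.1 and 12.2 they take the withdrawn subject's group and are not randomised, so enrolment number alone does not define a randomised set.
3. For between-group ratios use 0.5 LLOQ in both groups, so that each ratio equals the ratio of the tabulated GMTs. Limit the LLOQ-in-denominator rule, in the SAP and in Protocol 12.3, to within-subject fold-rise.
4. State with the results that an interval including 1 does not show that a fifth dose adds nothing. Protocol 6.5 gives every subject four vaccinations, so no arm tests a fifth.

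The cost is a SAP amendment, best made before the database is released for analysis (Protocol 16.2), a small amendment to Protocol 12.1 and 12.3 that needs IRB approval (Protocol 15.2), and a few extra table columns from RFFIT data already planned. The downside is visibly wide intervals, probably widest for chloroquine against concurrent controls.

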#### 3.1.2 Secondary Study Objective

To evaluate GMT over protective titer prior to third dose and fourth dose and 28 days post fourth dose of PCECV.

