# 3.2.2 Secondary Endpoint (Immunogenicity)

GMT by RFFIT prior to third or fourth dose of rabies vaccine and 28 days post fourth vaccine in prophylaxis groups vs control group.

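### The secondary objective refers to a protective titre that the SAP never defines, and no endpoint or planned table applies one, so the number of subjects below the adequate level will not be reported

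*SAP*

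**What the plan says.** Protocol 3.1.2 gives the secondary objective as "To evaluate GMT over protective titer prior to third dose and fourth dose and 28 days post fourth dose of PCECV". The SAP repeats it with a trivial change of wording: "To evaluate GMT over protective titer prior to third dose, fourth dose and 28 days post fourth dose of PCECV". Neither place gives a value for the protective titre.

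The only levels in the documents are in protocol 8.2.1. It says that the WHO "guideline of 0.5 International Units per milliliter (IU/mL) is used as an adequate response to rabies vaccination", and it names alongside this an ACIP level of "complete neutralization at a serum dilution of 1:5 in the RFFIT test". It does not rank the two, and nothing links either of them to the phrase used in the objective.

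The matching endpoint in protocol 3.2.2 is "GMT by RFFIT prior to third or fourth dose of rabies vaccine and 28 days post fourth vaccine in prophylaxis groups vs control". It is a comparison with control and contains no threshold. The primary endpoint in 3.2.1 is likewise GMT against control.

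The SAP plans two titre tables. The primary one, broken down by group, is "A table that presents the total number of per-protocol subjects and GMT against rabies at 14 days post completion of four doses of vaccine". The secondary one is "A table that presents, by group, the total number of per protocol subjects and the GMT against rabies prior to the third and fourth dose", and 28 days after dose 4. Each contains a count of per-protocol subjects and a GMT, and nothing else is listed.

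**The concern.** An objective that mentions a protective titre needs a stated titre and an output that uses it. Here the chain breaks twice: the term has no value, and neither the endpoint nor the table refers to one.

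The missing output matters because a geometric mean describes the centre of a group. A group GMT well above 0.5 IU/mL is compatible with every member being above that level, and also with a minority being below it. The two pictures bear differently on the study's practical question, which protocol 2.2 puts as whether a fifth dose adds anything for people on malaria prophylaxis. N and GMT alone cannot tell them apart.

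**Working it through.** **Text check.** The plan states no figure on this point, so there is nothing to reproduce. The places to compare are:

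| Place | What it uses | Threshold applied? |
|---|---|---|
| Protocol 3.1.2 and the SAP secondary objective | GMT relative to a protective titre | Mentioned, no value |
| Protocol 8.2.1 | 0.5 IU/mL; full neutralisation at 1:5 | Defined, not tied to an endpoint |
| Protocol 3.2.1 and 3.2.2 | GMT against control | No |
| SAP primary and secondary tables | N and GMT by group | No |
| SAP fold-rise and titre ratio | Rule for values below LLOQ only | No |
| SAP outlier plots and tests | Individual titres | No |
| SAP optional exploratory analyses | Unspecified | None named |

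**What N and GMT leave open.** The documents give no expected GMT, SD or LLOQ, so every titre and SD below is an assumption. For log-normal titres:

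share below 0.5 IU/mL = Φ((log10 0.5 − log10 GMT) / SD)

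Example with GMT 2 and SD 0.3: log10 0.5 − log10 2 = −0.301 − 0.301 = −0.602; −0.602 / 0.3 = −2.007; Φ = 2.2%.

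| Assumed GMT (IU/mL) | SD 0.3 log10 | SD 0.6 log10 |
|---|---|---|
| 1 | 15.8% | 30.8% |
| 2 | 2.2% | 15.8% |
| 4 | 0.1% | 6.6% |
| 10 | under 0.01% | 1.5% |

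At GMT 10 the worst case is 0.015 × 25 = about 0.4 of a subject per group. At GMT 2 it is 0.158 × 25 = about 4 subjects.

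**The same without log-normality.** Take 25 subjects, 5 at 0.25 IU/mL and 20 at 5 IU/mL. Then log10 GMT = (5 × (−0.602) + 20 × 0.699) / 25 = 0.439, so the GMT is 2.75 IU/mL. That is 2.75 / 0.5 = 5.5 times the threshold, with 20% of the group below it.

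**What a proportion would deliver.** Protocol 12.2 plans 100 subjects allocated 1:1:1:1, so 25 per group. Exact (Clopper-Pearson) 95% CIs for the share at or above the threshold:

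- 25/25: 86.3% to 100%
- 24/25: 79.6% to 99.9%
- 22/25: 68.8% to 97.5%
- 20/25: 59.3% to 93.2%
- 20/20, if per-protocol exclusions leave 20 (assumed): 83.2% to 100%

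If the true share below were 5%, the chance of seeing at least one such subject among 25 is 1 − 0.95^25 = 72%. At 10% it is 1 − 0.90^25 = 93%.

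**The case against.** The objective is worded in terms of the GMT, a group summary. On that wording, a table of group GMTs read beside 0.5 IU/mL does address it in part. This stands. A reader might infer that the secondary objective goes wholly unanswered, but the wording does not support that. It could mean a ratio of GMT to threshold, a group GMT above the threshold, or subjects above it, and the documents do not say which.

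A reader might also infer that the primary endpoint is wrong because it is not a proportion. The documents do not support this either. The primary objective compares GMT with control and mentions no protective titre, and the study is declared descriptive and exploratory.

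The SAP does look at individual titres through histograms, box plots or normal probability plots and a sensitivity analysis for outliers, and it permits further exploratory work. A cluster of low responders could surface there. Bootstrapped standard errors may be reported, and confidence intervals are mentioned among the exploratory methods; with either, a reader could approximate a spread. But these routes are partly optional, none applies a threshold, and neither planned table lists them. The outlier rules may also lead to statistics with low values removed, which is not the same as counting subjects below an adequate level.

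Finally, 25 per group is small. Even 5/25 against 0/25 below the threshold gives a two-sided Fisher p of 0.0502. That is a reason to report the proportion descriptively with its interval. It is not a reason to omit it.

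**Conclusion.** The point holds in a limited form. The secondary objective uses a term that the SAP does not define, and no endpoint or planned table applies either level in protocol 8.2.1. The planned tables therefore cannot show how many subjects are below the adequate level at any time point.

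How much this hides depends on titres that the documents do not give. Under the assumed log10 SDs of 0.3 to 0.6, it ranges from up to about 31% of a group at a GMT of 1 IU/mL to 1.5% or less at a GMT of 10. The figures show that the problem is possible. They do not show that any subject will be below the level, and a reader should not infer that.

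Nor do the documents establish 0.5 IU/mL as the protective titre with 1:5 in second place. Protocol 8.2.1 names both without ranking them, so the choice is the sponsor's to state.

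**What to change.** In the SAP, before the analysis:

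1. Define the protective titre by reference to protocol 8.2.1. One workable choice is 0.5 IU/mL, with the 1:5 criterion also reported.
2. In the secondary table add, by group and for each per-protocol set, n/N (%) of subjects at or above that titre with an exact 95% CI, before dose 3, before dose 4 and 28 days after dose 4.
3. Give the same column 14 days after dose 4 as a supportive descriptive output. Leave the primary GMT endpoint in protocol 3.2.1 unchanged.

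The cost is a short SAP revision and one column per table. RFFIT is already planned at all four time points, so no new samples, subjects or tests are needed. Keeping the change in the SAP also avoids a late amendment of the protocol endpoints, which would need IRB approval under protocol 15.2. The drawback is that the intervals will be visibly wide (25/25 still allows a true share as low as 86.3%), so the column should be labelled descriptive and not used to claim that groups are equivalent.
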